#### **Exclusion:**

- 1. Females who are pregnant or lactating or planning to become pregnant during the study period.
- 2. Treatment with the following products:
  - a. Topical acne treatments (retinoids, antibiotics, benzoyl peroxide, azelaic acid, resorcinol, salicylates, α-hydroxy/glycolic acid), or other topical facial medication (antifungals, steroids, anti-inflammatories) on the treatment area in the 14 days prior to the Baseline Visit, including prescription and non-prescription products.
  - b. Systemic corticosteroids, systemic acne treatments including systemic antibiotics used for treatment of acne, potential photosensitizing agents (thiazides, phenothiazines), spironolactone, flutamide, or immunosuppressant drugs in the 30 days prior to the Baseline Visit.
  - c. Systemic retinoid use (including high dose vitamin A > 10,000 units per day) in the 180 days prior to the Baseline Visit.
  - d. Undertaken certain facial procedures such as chemical peel, laser treatment, photodynamic therapy, acne surgery, cryodestruction or chemodestruction, x-ray therapy, intralesional steroids, dermabrasion, or depilation (except eyebrow shaping) in the 30 days prior to the Baseline Visit. After the subject is enrolled in the study, eyebrow shaping (except for tweezing) is prohibited.
  - e. Treatment with a medication or procedure that, in the opinion of the investigator, would put the subject at unacceptable risk for participation in the study or may interfere with evaluations in the study.
  - f. Treatment with an investigational product or device in the 30 days prior to the Baseline Visit.
- 3. Known allergic reaction to retinoids or tazarotene or any of the other ingredients of these products. The inactive ingredients are sodium lauryl sulphate, stearyl alcohol, cetyl alcohol, gluconolactone, Vitamin E polyethylene glycol succinate, glycerin, carbomer P 971, propylparaben, methylparaben, edetate disodium, butylated hydroxytoluene, medium-chain triglyceride, trolamine, and purified water.
- 4. Presence of any facial skin disease or condition that would interfere with the study or place the subject at unacceptable risk including sunburn, rosacea, seborrheic dermatitis, perioral dermatitis, lupus, dermatomyositis, psoriasis, eczema, squamous cell carcinoma, acneiform

eruptions caused by medications, steroid acne, steroid folliculitis, bacterial folliculitis or any other facial disease or condition.

- 5. Excessive facial hair (i.e., heavy beard or mustache), facial tattoos or facial disfigurement that would interfere with study assessments.
- 6. Subjects with a serious and/or chronic medical condition such as chronic or active liver disease, renal impairment, heart disease, severe respiratory disease, rheumatoid arthritis, current malignancies, immunocompromised conditions, or any other disease that, in the opinion of the investigator, would interfere with the study or place the subject at unacceptable risk.
- 7. Subjects who have been treated for alcohol dependence or alcohol or drug abuse in the year prior to the Baseline Visit.
- 8. Subjects who have been in another investigational trial within 30 days of the Baseline Visit.
- 9. Subjects may not have a personal relationship with any member of the study staff or be part of the staff at the medical practice.

## **Investigational Product, Dose and Mode of Administration:**

DFD-03 Lotion (0.1% tazarotene) or Vehicle Lotion

Subjects will apply a quarter (U.S coin) size amount of the study product all over the moistened face and rub it into the skin until foamy. Care should be taken to avoid the areas around the eyes, mouth, and nostrils. After being left on for 1 minute, the subject will rinse off the product by thoroughly rinsing with warm water for about 30 seconds. This procedure will be followed twice daily, in the morning and at bedtime, approximately 12 hours apart.

For those subjects treating chest and/or back, including shoulders at selected site(s), an additional 1-2 quarter size amount of the study product may be used over other affected areas and applied similarly as on the face.

## **Duration of Treatment and Study:**

Subjects will treat the entire face, including the nose (and only at selected site(s), chest and/or back, including shoulders) twice daily for 12 weeks. The total study duration including the screening period will be approximately 12 to 20 weeks.

### Reference and Control Products, Dose and Mode of Administration:

Tazorac (tazarotene) Cream, 0.1% or Vehicle Cream

Approximately 1 g (pea size amount) of investigational product will be applied over the entire face once daily at bedtime and left on overnight.

At selected site(s), an additional amount of 1-2 g investigational product will be applied to chest and/or back (including shoulders), if applicable and left overnight.

### **Criteria for Evaluation:**

## Safety criteria:

Safety variables include local tolerability/application site reaction occurrence and adverse events. Comparison of local tolerability and safety of DFD-03 Lotion with Tazorac Cream will be the primary endpoint for this study.

Local tolerability/application site reactions include dryness, non-lesional erythema, peeling, stinging/burning, and pruritus and will be assessed at each study visit from Baseline through End of Study. The reactions on the face will be assessed separately from those on the chest and/or back, including shoulders (if applicable). Other safety variables include physical examination and vital signs (blood pressure and pulse rate).

## Efficacy criteria:

The following efficacy variables will be summarized using descriptive statistics for both the ITT and PP populations.

- The IGA success rate at Week 12 (an IGA score of 0 (Clear) or 1 (almost clear) with at least a 2-grade reduction from baseline)
- Absolute change from baseline in inflammatory and non-inflammatory lesion counts on the face at the Week 12 visit.
- Percent change from Baseline to Week 12 in inflammatory lesion counts on the face
- Change from Baseline to Week 12 in CADI

**Table 1: Study Schedule** 

	Visit 11	Visit 21	Visit 3	Visit 4	Visit 5
	Screen Day -60 to 0	Day 1 Baseline	Week 4  Day 28	Week 8  Day 56	Week 12  Day 84
Informed consent/assent	X				
Inclusion and exclusion criteria	X	X			
Medical (including acne) history/prior & concomitant medications	X	X			
Collect demographic data	X				
Fitzpatrick Skin Type Assessment		X			
Physical Examination (including height and weight at Baseline Visit only)		X			X
Vital signs assessment (Blood Pressure & Pulse Rate)	X	X	X	X	X
Update concomitant medications			X	X	X
Urine pregnancy test 	X	X	X	X	X
Randomization		X			
Dispense/redispense study product		X	X	X	
Weigh study product bottles prior to dispensing and used bottles upon return		X	X	X	X
Initiate treatment		X			
Dispense/review/ collect study diary		X	X	X	X
Review subject instructions		X	X	X	
Collect empty bottles			X	X	X
Evaluate IGA on face	X	X	X	X	X
Count inflammatory and non-inflammatory lesions on face	X	X	X	X	X
Count inflammatory and non-inflammatory lesions on the chest and/or back including shoulders (if applicable) 		X	X	X	X
Assess for any local cutaneous tolerance/application site reactions  on face and, if applicable, separately for the chest and/or back including shoulders 		X	X	X	X
CADI questionnaire		X	X	X	X
Evaluate compliance			X	X	X
Adverse event assessment		X	X	X	X
End of study					X

<sup>1 Visit 1 and Visit 2 may be combined if no washout is required, but should not be separated by more than 60 days

<sup>2 Visit window  $\pm$  3 days

Visit window ± 5 days
 Visit window ± 5 days
 For all females regardless of reproductive potential
 Dryness, non-lesional erythema, peeling, stinging, burning, itching
 For the selected site(s) that will randomize subjects who will be treating chest and/or back (including shoulders)

## LIST OF ABBREVIATIONS

Abbreviations	Description
AE	adverse event
BP	blood pressure
CADI	Cardiff Acne Disability Index
CFR	Code of Federal Regulations
eCRF	electronic case report form
CRO	contract research organization
EDC	electronic data capture
FDA	Food and Drug Administration
GCP	Good Clinical Practice
hCG	human chorionic gonadotropin
IGA	Investigator's Global Assessment
IRB	institutional review board
ITT	intent-to-treat
LOCF	last observation carried forward
MedDRA	Medical Dictionary for Regulatory Activities
PHI	protected health information
PP	per-protocol
PT	preferred term
SAE	serious adverse event
SGA	Subject's Global Assessment
SOC	system organ class
TEAE	treatment-emergent adverse event

## LIST OF DEFINITIONS

**Term Definition** 

EDC Electronic Data Capture is a computerized system designed for

the collection of clinical data in electronic format including the

eCRF.

Screening Visit

(Visit 1)

The day a subject is screened according to the protocol inclusion/exclusion criteria after having provided informed consent/assent. The screening visit may occur on the same day

as Visit 2 (Baseline) for this study.

Screened Subject A subject who has signed informed consent/assent.

Screening Number A screening number will be assigned by the site at Visit

1/Screening, consisting of a 3-digit site number followed by a 3-digit sequential number for each subject in chronological order (e.g., 801-001, where the site number is 801 and the first

screened subject is 001)

Baseline Visit (Visit 2/Day 1)

The day of randomization and the first study product application. The first study product application is done at the

site by the subject during the visit.

Subject Number A unique subject number will be assigned to each subject. The

randomization number (subject kit number) will be designated as the subject number. The subject will maintain the same subject number and treatment assignment throughout the study.

Subject numbers will be assigned immediately prior to

dispensing study medication and will be assigned starting with

the lowest available number at the study site.

Study product(s) Investigational product(s)

### 1 INTRODUCTION

Tazarotene, an acetylenic retinoid, is a prodrug that undergoes rapid and complete metabolism to its active metabolite tazarotenic acid (Chandraratna, 1996). Retinoids are a class of keratolytic drugs derived from retinoic acid used for the treatment of acne and psoriasis. Several synthetic retinoids have been developed for topical treatment of acne.

Tazarotene was initially developed in gel formulation and subsequently in cream and foam formulations. Products containing tazarotene have been proven to be effective in the treatment of acne vulgaris and psoriasis, as well as being effective in the mitigation (palliation) of facial fine wrinkling, facial mottled hyper- and hypopigmentation, and benign facial lentigines.

[name] has developed DFD-03 Lotion, a new formulation containing 0.1% tazarotene for the topical treatment of acne vulgaris. This new product is intended to be used as a face wash twice daily. Treatment use will begin by applying a generous amount of product to moistened affected skin, rubbing until foamy, and then rinsing with water after 1 minute.

Acne vulgaris is characterized by a mixture of inflammatory lesions (papules, pustules, and nodular cystic lesions) and non-inflammatory lesions (open and closed comedones) (Shalita, 2004). The four primary factors contributing to acne are abnormal follicular epithelial desquamation, hyperactivity of the sebaceous glands, proliferation of *Propionibacterium acnes*, and perifollicular inflammation.

Currently available treatments for acne vulgaris include oral and topical antibiotics, topical benzoyl peroxide, topical salicylic acid, topical adapalene, topical azelaic acid, topical dapsone, oral and topical retinoids (including tazarotene), and phototherapy.

Tazarotene is a well-characterized active ingredient, and many studies have been conducted on its pharmacology, toxicology and clinical efficacy and safety (Fabior Prescribing Information, Tazorac Cream Prescribing Information).

Tazarotene is characterized by the FDA as a Category X drug, indicating that it may or can cause fetal harm when administered to a pregnant woman and is contraindicated in women who are or may become pregnant (Menter, 2000). At least 6 women are known to have become pregnant during clinical studies with tazarotene and all reported the birth of healthy babies, although the timing and extent of exposure in relation to the gestation time are unknown in these cases.

The purpose of this study is to assess the safety and local tolerability of DFD-03 Lotion 0.1% compared to Tazorac (tazarotene) Cream, 0.1% Cream for topical treatment of acne vulgaris for 12 weeks.

More information about DFD-03 Lotion 0.1% can be found in the Investigator's Brochure.

### 2 ETHICALCONSIDERATIONS

#### 2.1 Institutional Review Board Review

The protocol, protocol amendments, subject recruiting materials, the informed consent form, and any other materials provided to subjects must be approved by an institutional review board (IRB) operating in compliance with 21 Code of Federal Regulations (CFR) Part 56. A copy of

the approval letter must be received by the sponsor or contract research organization (CRO) prior to shipment of drug supplies to the site.

Records of the IRB's review and approval of all documents pertaining to the study must be kept on file by the investigator and are subject to sponsor and Food and Drug Administration (FDA) inspection at any time.

## 2.2 Ethical Conduct of Study

The investigator will ensure that this study is conducted in full conformity with the principles set forth in 21 CFR Part 50 – Protection of Human Subjects and in the Declaration of Helsinki (2013) (see Appendix 1).

### 2.3 Informed Consent

Written informed consent must be obtained before a subject can participate in the study, prior to performing any study related procedures, and before withdrawal of any therapies prohibited during the study. Informed consent is a process that is initiated prior to the subject's agreement to participate in the study and continuing throughout the subject's study participation. The process involves an extensive discussion with the subject about the study procedures and the risks and possible benefits of participation in the study.

For subjects under the age of majority in the state they are enrolled, the subject's parent or legal guardian will be required to sign the informed consent form and the subject will sign an IRB-approved "information and assent" form before the subject is enrolled into the study.

A copy of the signed consent form and information and assent form (when applicable) will be given to every subject and the original will be maintained with the subject's records.

## 2.4 Selection of Investigators

Investigators for the study should be board-certified dermatologists licensed in the state where the study is being conducted, with knowledge and understanding of Good Clinical Practice (GCP) and experience in treating acne vulgaris. In some cases, qualified physicians who are not board-certified dermatologists may participate based on training and experience in the treatment of acne vulgaris. Sub-investigators may be licensed physicians, physician assistants, or nurse practitioners with experience in treating acne vulgaris or in dermatology and a good understanding of GCP. Investigators may delegate study tasks to other site personnel as long as they are qualified to perform the task.

#### 3 STUDY OBJECTIVES

The objectives of this study are to determine the safety and local tolerability of DFD-03 (tazarotene) Lotion 0.1% and to compare it with Tazorac (tazarotene) 0.1% Cream in the topical treatment of acne vulgaris for 12 weeks.

## 4 STUDY DESIGN

This will be a multicenter, randomized, double-blind, parallel-group, active-controlled study. Approximately 150 subjects with mild to moderate facial acne vulgaris will be randomized in a

2:2:1:1 ratio to treatment with DFD-03 (tazarotene) Lotion 0.1%, Tazorac (tazarotene) Cream, 0.1%, Vehicle Lotion, or Vehicle Cream. During the 12-week treatment period subjects randomized to DFD-03 Lotion or Vehicle Lotion will use the study drug twice daily with approximately 12 hours between applications. Subjects randomized to Tazorac Cream or Vehicle Cream will use the study drug once daily in the evening.

At selected site(s), subjects with acne lesions of any severity on the chest and/or back (including shoulders) may be enrolled provided they have met all inclusion criteria including mild to moderate acne on the face and have not met any exclusion criteria and will treat all areas affected with acne on the face, chest and/or back, including shoulders, if applicable. Up to 12 subjects with acne involvement on the face, chest and/or back including shoulders will be randomized to treatment with either DFD-03 (tazarotene) Lotion 0.1%, Tazorac (tazarotene) Cream, 0.1%, Vehicle Lotion or Vehicle Cream in a ratio of 2:2:1:1.

Also, there will be selected site(s) that will enroll approximately 8 subjects who are 9 years of age to 11 years of age. They will be randomized to DFD-03 group only in a 1:1 ratio of DFD-03 (tazarotene) Lotion 0.1% to Vehicle Lotion. The total number of approximately 150 subjects in the study will include up to 12 subjects with acne on the chest and/or back, and approximately 8 subjects in the age group of 9-11 years.

Safety variables include local tolerability/application site reaction occurrence and treatment-emergent adverse events (TEAEs). The primary safety endpoint will be the comparison of local tolerability/application site reactions and safety of DFD-03 Lotion with Tazorac Cream. Local tolerability/application site reactions include dryness, non-lesional erythema, peeling, stinging/burning, and pruritus and will be assessed (separately for the face and the chest and/or back) at each study visit from Baseline through End of Study. Other safety variables include vital signs (blood pressure and pulse rate). A physical examination will be performed at Baseline and at the End of Study Visit. Urine pregnancy tests will be performed at Screening, Baseline and at every visit through Week 12 for all female subjects.

The investigator will assess efficacy by using an Investigator's Global Assessment scale (IGA, 5-point scale) and by counting the number of inflammatory and non-inflammatory lesions on the face at Screening, Baseline and Weeks 4, 8, and 12. Lesion counts will also be done separately for the chest and/or back (including shoulders), where applicable for those selected site(s).

The Cardiff Acne Disability Index (CADI) will be used to assess the quality of life in all subjects at Baseline (Day 1) and at Weeks 4, 8 and 12.

### 5 SELECTION OF STUDY POPULATION

## 5.1 Number of Subjects

Approximately 150 subjects will be randomized at 10 centers to have 120 subjects who complete the study.

### 5.2 Inclusion Criteria

1. Subject understands the study procedures, is willing to comply with the study procedures and required visits, and agrees to participate by giving written informed consent.

- Subjects under the legal age of consent must provide written assent and must have the written informed consent of their legal guardian.
- 2. Subject (or legal guardian) must be willing to authorize use and disclosure of protected health information collected for the study.
- 3. Subject must be at least 12 years of age.
  - At selected site(s), a total of approximately eight subjects 9-11 years of age will be enrolled into the 2 arms of DFD-03 lotion group (active and vehicle).
- 4. Female subjects must be having their menstrual period at the Baseline Visit (as reported by the subject), except for subjects using hormonal contraceptives that preclude menstrual periods, if the subject is premenarchal, is postmenopausal for at least 12 months prior to baseline, is surgically sterilized (i.e. tubal ligation) or if the subject is without a uterus and /or both ovaries.
- 5. A clinical diagnosis of facial acne vulgaris with an Investigator's Global Assessment (IGA) score of 2 (mild) to 3 (moderate) at Baseline.
  - At selected site(s), up to twelve subjects with acne lesions on the chest and/or back (including shoulders) in addition to those on the face will treat their back and/or chest (including shoulders) in addition to their face.
- 6. Inflammatory lesion count (papules and pustules) of at least 20 on the face, including the nose, at Baseline.
  - This criteria is not applicable to the 9-11 years age group as long as subjects have an IGA score of 2 (mild) to 3 (moderate) at Baseline.
- 7. Non-inflammatory lesion count (closed and open comedones) of at least 25 on the face, including the nose, at Baseline.
  - This criteria is not applicable to the 9-11 years age group as long as subjects have an IGA score of 2 (mild) to 3 (moderate) at Baseline.
- 8. No more than 2 nodulocystic lesions on the face, including the nose, at Baseline.
- 9. Females, regardless of childbearing potential:
  - a. Must have a negative urine pregnancy test at Screening and Baseline. Test must have a sensitivity of at least 25 mIU/mL for  $\beta$ hCG.
  - b. If sexually active, must be on or use an acceptable method of birth control.

### Acceptable methods of birth control include:

- hormonal methods\* or intrauterine device in use  $\geq 90$  days prior to Baseline; or
- partner has had a vasectomy at least 90 days prior to Baseline; or
- barrier methods plus spermicide; or
- Essure® that has been in place for at least 3 months before the screening visit with radiograph confirmation of fallopian tube blockage.

\*Hormonal methods: If on hormonal contraceptives, must have been on the same hormonal contraceptive product for 3 months (90 days) prior to Baseline and continued on same method and dose throughout the duration of the study. If subject had used hormonal birth control and had stopped, this should have occurred more than 6 months prior to Baseline.

**Exception:** Sexually inactive female subjects are not required to practice a reliable method of contraception and may be enrolled at the investigator's discretion provided that they are counseled to remain sexually inactive for the duration of the study and understand the possible risks involved in getting pregnant during the study. An abstinent female must agree that if she becomes sexually active during the study she will use an acceptable form of contraception such as a barrier method with spermicide. Females who are surgically sterilized [e.g. hysterectomy, bilateral tubal ligation, bilateral oophorectomy] at least 1 year prior to Baseline or have been postmenopausal for at least 1 year prior to Baseline are not required to practice a reliable method of contraception.

- 10. Subjects agree not to use any product on the face during the entire course of study except for non-medicated, investigator-approved cleanser, sunscreen, face wash, and make-up as instructed by the investigator. Subjects should continue to use these investigator-approved products for the duration of the study and should avoid any changes in these consumer products.
- 11. Subjects must be willing to comply with sun avoidance measures for the face (as well as back/chest including shoulders, if applicable) including use of investigator-approved sunscreen and/or hats, have limited sun exposure time, and have no tanning bed use.
- 12. Subject must be in good general health as determined by the investigator and supported by the medical history, physical examination, and normal or not clinically significant abnormal vital signs (blood pressure and pulse). Subjects are eligible if:
  - Systolic blood pressure (BP) < 160 and > 85 mmHg
  - Diastolic BP < 100 and > 50 mmHg
  - Pulse 50 to 100 bpm inclusive for adults; up to 110 bpm for subjects < 18 years of age;

### 5.3 Exclusion Criteria

- 1. Females who are pregnant or lactating or planning to become pregnant during the study period.
- 2. Treatment with the following products:
  - a. Topical acne treatments (retinoids, antibiotics, benzoyl peroxide, azelaic acid, resorcinol, salicylates, α-hydroxy/glycolic acid), or other topical facial medication (antifungals, steroids, anti-inflammatories) on the treatment area in the 14 days prior to the Baseline Visit, including prescription and non-prescription products.
  - b. Systemic corticosteroids, systemic acne treatments including systemic antibiotics used for treatment of acne, photosensitizing agents (thiazides, phenothiazines), spironolactone, flutamide, or immunosuppressant drugs in the 30 days prior to the Baseline Visit.

- c. Systemic retinoid use (including high dose vitamin A > 10,000 units per day) in the 180 days prior to the Baseline Visit.
- d. Undertaken certain facial procedures such as chemical peel, laser treatment, photodynamic therapy, acne surgery, cryodestruction or chemodestruction, x-ray therapy, intralesional steroids, dermabrasion, or depilation (except eyebrow shaping) in the 30 days prior to Baseline visit. After the subject is enrolled in the study, eyebrow shaping (except for tweezing) will also be prohibited.
- e. Treatment with a medication or procedure that, in the opinion of the investigator, would put the subject at unacceptable risk for participation in the study or may interfere with evaluations in the study.
- f. Treatment with an investigational product or device in the 30 days prior to the Baseline Visit.
- 3. Known allergic reaction to retinoids or tazarotene or any of the other ingredients of these products. The inactive ingredients are sodium lauryl sulphate, stearyl alcohol, cetyl alcohol, gluconolactone, Vitamin E polyethylene glycol succinate, glycerin, carbomer P 971, propylparaben, methylparaben, edetate disodium, butylated hydroxytoluene, medium-chain triglyceride, trolamine, and purified water.
- 4. Presence of any facial skin disease or condition that would interfere with the study or place the subject at unacceptable risk including sunburn, rosacea, seborrheic dermatitis, perioral dermatitis, lupus, dermatomyositis, psoriasis, eczema, squamous cell carcinoma, acneiform eruptions caused by medications, steroid acne, steroid folliculitis, bacterial folliculitis or any other facial disease or condition.
- 5. Excessive facial hair (i.e., heavy beard or mustache), facial tattoos or facial disfigurement that would interfere with study assessments.
- 6. Subjects with a serious and/or chronic medical condition such as chronic or active liver disease, renal impairment, heart disease, severe respiratory disease, rheumatoid arthritis, current malignancies, immunocompromised conditions, or any other disease that, in the opinion of the investigator, would interfere with the study or place the subject at unacceptable risk.
- 7. Subjects who have been treated for alcohol dependence or alcohol or drug abuse in the year prior to the Baseline Visit.
- 8. Subjects who have been in another investigational trial within 30 days of the Baseline Visit.
- 9. Subjects may not have a personal relationship with any member of the study staff or be part of the staff at the medical practice.

Subjects must not use the medications or procedures shown in Table 2 for the period specified before the Baseline Visit (Visit 2). Table 2 also indicates whether the medications or procedures are allowed or prohibited during the study (after the Baseline Visit).

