**Table 2: Washout Periods (Prior to Baseline - Visit 2)** 

Product	Washout Period	During Study
Topical acne treatments (retinoids, antibiotics, benzoyl peroxide, azelaic acid, resorcinol, salicylates, α-hydroxy/glycolic acid), or other topical facial medication (antifungals, steroids, anti-inflammatories) on the treatment area, including prescription and non-prescription products	14 days	Prohibited
Systemic corticosteroids, systemic acne treatments including systemic antibiotics used for acne treatment, photosensitizing agents (thiazides, phenothiazines), spironolactone, flutamide, or immunosuppressant drugs	30 days	Prohibited
Other investigational product or device		
Systemic antibacterials	Allowed except systemic antibiotics used for acne treatment which will require a 30- day washout period	Up to 10 days allowed for indications other than acne
Facial procedures such as chemical peel, laser treatment, photodynamic therapy, acne surgery, cryodestruction or chemodestruction, x-ray therapy, intralesional steroids, dermabrasion, or depilation (except eyebrow shaping)	30 days	Prohibited [Eyebrow shaping (except for tweezing) is prohibited during the study]
Systemic retinoid (including high dose vitamin A > 10,000 units per day)	180 days	Prohibited

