3.2. Study Endpoints

3.2.1. Primary Endpoints

The primary safety endpoints are:

- Local Cutaneous Safety Evaluation Data (dryness, non-lesional erythema, peeling, stinging, burning, and itching). Reactions on the face were assessed separately from those on the chest/back/shoulders.
- Treatment-Emergent Adverse Events (TEAEs).

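### The listed skin-disease and procedure exclusions, and the procedure row of Table 2, stop at the face, although up to 12 subjects also treat and are graded on the chest, back or shoulders

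*Protocol*

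**What the plan says.** Protocol Section 4 provides that, at selected sites, "subjects with acne lesions of any severity on the chest and/or back (including shoulders) may be enrolled". These subjects, up to 12 of about 150, apply study product to every affected area. Section 7.6 has dryness, erythema, peeling, stinging, burning and itching graded on the trunk with the same scales as on the face. SAP 3.2.1 lists the local cutaneous data first among the primary safety endpoints and adds: "Reactions on the face were assessed separately from those on the chest/back/shoulders".

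The entry rules differ in how far down the body they reach. Exclusion 4 opens "Presence of any facial skin disease or condition that would interfere with the study or place the subject at unacceptable risk including sunburn, rosacea". Exclusion 2d covers subjects who have "Undertaken certain facial procedures such as chemical peel, laser treatment, photodynamic therapy, acne surgery" and similar interventions, including depilation, in the 30 days before Baseline. The matching row of Table 2, which also carries the prohibition during the study, begins "Facial procedures such as chemical peel, laser treatment, photodynamic therapy, acne surgery". Exclusion 5 (hair, tattoos, disfigurement) is facial as well. The SAP repeats these criteria in its summary and in the notes to Listing 16.2.2.1.

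Other rules do reach the trunk. Inclusion 11 states: "Subjects must be willing to comply with sun avoidance measures for the face (as well as back/chest including shoulders, if applicable". Exclusion 2a is tied to the treatment area, although its second limb still speaks of topical facial medication.

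**The concern.** A subject who treats the trunk may have sunburned, eczematous or recently waxed skin there without meeting any exclusion that names those conditions. After Baseline, Table 2 prohibits the listed procedures only on the face. Erythema, peeling or stinging that follows trunk depilation or laser treatment looks like product intolerance on these scales. It would be graded in the trunk tolerability data and, if worse than Baseline, recorded as an AE. TEAEs are themselves a primary safety endpoint. What is at stake is whether the reactions of a very small trunk cohort can be attributed to product. The documents give no reason why treated trunk skin should be handled differently from treated facial skin.

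**Working it through.** The plan states no figure on this point, so the check is mainly a comparison of texts.

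**Anatomical scope of each rule**

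| Rule | Scope as written | Fixed or discretionary |
|---|---|---|
| Exclusion 2a and first row of Table 2 (topicals, 14 days) | Treatment area; second limb still says facial | Fixed window |
| Exclusion 2d and Table 2 procedure row | Face | Fixed 30 days; prohibited during study |
| Exclusion 2e (medication or procedure) | Any site | Investigator opinion, at entry |
| Exclusion 4 (skin disease) | Face | Listed, but conditional on interference or risk |
| Exclusion 5 (hair, tattoos) | Face | Conditional on interference |
| Exclusion 6 (other disease) | Any site | Investigator opinion |
| Inclusion 11 (sun avoidance) | Face and trunk | Willingness to comply, not sunburn already present |

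**At entry.** Trunk depilation can be caught by 2e and trunk eczema by 6, both by opinion. Acute trunk sunburn is harder to place: 2e concerns treatments, and 6 opens with serious or chronic conditions and ends with other disease.

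**After Baseline.** Exclusion 2e is an entry criterion. The during-study rule for procedures is in Table 2 and names only the face, so no explicit rule prohibits trunk depilation, peel or laser treatment.

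**In the analysis.** Protocol 11.5.2 and SAP 9.2 plan a second summary without subjects who had signs or symptoms at Baseline. That deals with conditions visible on Day 1. It cannot remove a reaction to a later procedure, or a flare of a condition that was quiet on Day 1.

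**Size.** Inputs: up to 12 trunk subjects of about 150 (Protocol Section 4); allocation 2:2:1:1, giving arms of 50, 50, 25 and 25 (Section 6.4).

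- Trunk cohort: 12 × 2/6 = 4 per active arm and 12 × 1/6 = 2 per vehicle arm; 12/150 = 8% of subjects.
- TEAE tables, not split by location: one subject moves an active arm by 1/50 = 2 percentage points and a vehicle arm by 1/25 = 4. The ceiling, with every trunk subject in an arm affected, is 4/50 = 8 or 2/25 = 8 points.
- For scale, the 95% half-width for a difference between two arms of 50 is 1.96 × √(2p(1 − p)/50). At p = 0.10 this is 0.118 and at p = 0.30 it is 0.180, so about 12 to 18 points. Section 8 gives 10% to 30% for the commonest reactions to the cream.
- Trunk scores alone: one subject is 1/4 = 25 points in an active arm or 1/2 = 50 in a vehicle arm. These values only reflect cells of 4 and 2; any single event would do the same.

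**The case against.** The strongest reply is that the gap is mostly covered. Exclusions 2e and 6 are not limited by site, and a chest waxed two days before erythema grading fits the limb of 2e on interference with evaluations. Exclusions 4 and 5 are themselves conditional, so for those two the face gains an illustrative list rather than an absolute bar. Trunk signs are scored before the first application, trunk symptoms are asked about for the preceding two weeks, an AE needs worsening from Baseline, and there are randomised vehicle arms. Section 6.7 restricts products only on the face, but Sections 6.2.3 and 6.6 and the topical row of Table 2 largely cover the trunk. Section 8.2 also requires the location of an AE to be recorded.

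Most of this stands, and it rules out several stronger readings:

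- A reader might infer that subjects with trunk sunburn or eczema are simply eligible. They are not; the investigator may exclude them. What is missing is an explicit, uniform rule.
- A reader might infer that pre-existing trunk conditions cannot be separated from product effects. The Baseline scores and the second summary answer much of that.
- A reader might infer that the facial comparison is contaminated. The documents provide for separate assessment of face and trunk.
- A reader might infer that the amendment overlooked these exclusions. The change list in SAP Section 2 names only inclusion criteria among the criteria changed, but its text is incomplete, so the documents do not show this.

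The reply does not answer the period after Baseline: discretion at entry and a summary based on Baseline signs have no effect on later procedures or flares.

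**Conclusion.** The concern holds as a limited inconsistency of scope. Exclusions 2d and 4 and the procedure row of Table 2 do not match the area that up to 12 subjects treat and on which they are graded. The consequence is an avoidable source of confounding in the trunk scores and, at about 2 points per subject in an active arm, in the TEAE tables. No frequency of trunk conditions or procedures is given, so the expected size is unknown; 8 points per arm is the ceiling if the cohort is full and allocated 4, 4, 2 and 2.

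The conclusion that the facial comparison is unaffected rests on face and trunk being tabulated separately. The SAP states that principle, but the shell for the local cutaneous tables has no location split and the only tolerance listing (16.2.8.4.1) is for the face. Importance is low to moderate: 8% of subjects at most, in a study that Protocol 11.1 describes as not powered for significance.

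**What to change.** Reconcile the anatomical scope of exclusions 2d and 4, the Table 2 procedure row and the second limb of 2a (with its Table 2 row) with the area each subject treats: the face and, where applicable, chest and/or back including shoulders. If the sponsor intends the trunk to be handled differently, say so and why. Exclusion 2a is not a clean model, because it still contains the facial wording. Exclusion 5 needs adapting rather than word-for-word substitution, since it defines excess hair by beard and moustache. Mirror the result in the SAP criteria lists, and show location in the tolerability tables and listings.

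The SAP is largely in the past tense, so enrolment may be complete. In that case, flag trunk skin conditions and trunk procedures before unblinding and mark the affected reactions and TEAEs. Source records may be needed: Section 6.6 requires eCRF entry of procedures used for other diseases or conditions, which may not capture cosmetic depilation.

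The cost is amendment wording, or one blinded data review. A few chest/back candidates among at most 12 may be screened out. They cannot be assumed to enter as face-only subjects, because Protocol Section 4 has these subjects treat all affected areas.
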